7.0 Study Calendar

We will conduct a prospective study that will require participants to complete a screening/baseline visit followed by 4-day active study period and a final follow-up visit. The active study may start anywhere up to 30 days after the initial study visit. Thus, participants may be active in the study for up to 35 days. Up to 50 healthy volunteers may be enrolled. We plan to conduct the study over a 24 month time period.

8.0 Reportable Events

All potential research concerns will be monitored by the study research team from the time of initiation until completion. Potential risks associated with this study include loss of confidentiality, discomfort associated with stool collections, or discomfort associated with dietary intervention. The study team will take care to recognize and minimize any discomfort that collecting stool or completing questionnaires may cause for participants. Inulin ingestion will be kept to a one-time ingestion of 10 grams and participants will be counseled appropriately prior to its use. Any potential adverse events will be followed by the study physician until they normalize. All serious events will be reported immediately to regulatory authorities and the Indiana University IRB. Any incidental findings that may require medical or professional intervention will be discussed with the participant by the study physician and the participant will be referred to the appropriate care team.

9.0 Data Safety Monitoring

The study PI ([name]) and all members of the study team will perform safety monitoring of all research subjects. Data quality, subject recruitment, subject accrual, subject retention, outcomes, procedures designed to protect privacy of subjects, outcomes, and adverse events data will be monitored by the PI and designated members of the study team on a regular basis.

10.0 Study Withdrawal/Discontinuation

Drop-outs may occur due to withdrawal of consent or because of discomfort related to study procedures. In order to compensate for withdrawals and loss to follow-up, up to 50 patients could be enrolled to meet the target of 30 completed volunteers.

11.0 Statistical Considerations

We plan to enroll 30 healthy volunteers. In order to compensate for withdrawals and loss to follow up, up to 50 patients could be enrolled. As the primary objective of this study is to describe the technical feasibility of measuring, sample size calculations are not based on the primary objective. Instead, the sample size estimation is based on secondary endpoints of the association between fecal SCFAs after inulin supplementation and fecal microbiota composition. Our sample size of 30 subjects provides an 80% power to detect a Pearson correlation of 0.5 based on the Fisher's z test at the 5% significance level. We consider the correlation of 0.5 an important correlation. Such a correlation is large but achievable based on data from a preliminary study of 14 healthy volunteers conducted by our lab, where the Pearson correlation between microbiota composition (e.g. individual taxa) and individual fecal SCFA levels were found to be above 0.5 for 5% of the taxa found in the stool sample.

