1.0 Objective(s)

1.1 Primary Objective: To conduct a proof-of-concept study demonstrating the ability to measure fecal inulin and short chain fatty acid content in stool after a one-time ingestion of a standardized 10-gram dose of dietary inulin.

1.2 Secondary Objective(s):

- 1.2.1** To assess associations of bowel symptoms with fecal inulin and SCFA content after a one-time ingestion of dietary inulin
- 1.2.2** To assess associations of individual factors (baseline dietary intake, demographics, body-mass index) with fecal inulin and SCFA content after a one-time ingestion of dietary inulin.
- 1.2.3** To examine characterize fecal microbiota composition following a one-time ingestion of dietary inulin and associations of microbiota composition with fecal inulin and SCFA content

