2.0 Outcome Measures/Endpoints

2.1 Primary Outcome Measures: Fecal inulin, total and individual fecal SCFAs

2.2 Secondary Outcome Measures: Bowel symptoms (stool frequency, stool form, ease of passage) based on a validated bowel diary, baseline dietary intake (Automated Self-Administered Dietary Assessment)

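### The 80% power behind n=30 belongs to one correlation test that the plan never identifies, and the open set of microbiota tests has no multiplicity rule

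*Combined protocol and SAP*

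**What the plan says.** Section 11.0 states that the primary, feasibility objective does not drive the sample size. Instead, the "sample size estimation is based on secondary endpoints of the association between fecal SCFAs after inulin supplementation and fecal microbiota composition". For that association, 30 subjects "provides an 80% power to detect a Pearson correlation of 0.5" using a Fisher's z "test at the 5% significance level". Sidedness is not stated.

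Two grounds are given for r=0.5. The first is importance: "We consider the correlation of 0.5 an important correlation". The second is that such a value is achievable, "based on data from a preliminary study of 14 healthy volunteers", in which correlations between individual taxa and individual SCFA levels were "above 0.5 for 5% of the taxa found in the stool sample".

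Other sections show how many tests could fall under this association:

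- **SCFAs.** Section 2.1 lists "Fecal inulin, total and individual fecal SCFAs". No single SCFA is picked out.
- **Microbiota.** Section 6.0 plans 16S taxa, richness and diversity indices, shotgun taxa, and qPCR targets to be selected from the study's own sequences. Taxa involved in SCFA biosynthesis are an example; none is named.
- **Days.** Sections 4.0 and 6.0 plan four consecutive 24-hour collections, with each daily specimen divided for both SCFA and microbiota assays.
- **Objective.** Section 1.2.3 covers "associations of microbiota composition with fecal inulin and SCFA content", so fecal inulin is also part of the set.

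No section names a primary pair, says how the four days are combined, or gives a family-wise or false-discovery rule.

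**The concern.** The power statement describes one test, but the analysis it supports is an unspecified number of tests. A reader cannot tell which comparison has 80% power or how a significant result will be judged.

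The two possible courses have different costs. If 5% is applied to every pair, chance findings accumulate and the microbiota results can be over-read. If the error rate is controlled, power at r=0.5 falls below the figure that justifies n=30, and real associations are missed. The plan does not choose. This matters more than usual for a secondary objective because the calculation is the only justification given for n=30.

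The pilot raises a separate question. With 14 people, sample correlations above 0.5 are not rare when nothing is associated, so a count of such taxa may say little about whether 0.5 is attainable.

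**Working it through.** **Inputs from the documents.** n=30, r=0.5, 5% level, Fisher's z, pilot of 14 with 5% of taxa above 0.5 (Section 11.0); four daily collections (Sections 4.0 and 6.0).

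**Assumed, because the documents do not give them.** The number of tests m, the share p1 of pairs with a true r of 0.5, and the false discovery level q. Ranges are shown.

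**1. The plan's own figure.** Power = Φ(atanh(r)·√(n−3) − z), where z is the two-sided critical value; the opposite tail is negligible.

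- atanh(0.5)·√27 = 0.5493 × 5.196 = 2.854
- Φ(2.854 − 1.960) = 81.4%
- Required n = ((1.960 + 0.842)/0.5493)² + 3 = 29.01, rounded up to 30

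The figure reproduces. A one-sided 5% test would give 88.7% and n=24, so two-sided is the reading that fits.

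**2. One pair, four days.** This needs no assumption about the number of taxa.

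- Unadjusted chance of at least one false positive: 5% if the days are fully correlated, 1 − 0.95⁴ = 18.5% if they are independent.
- Bonferroni, 0.05/4 = 0.0125: Φ(2.854 − 2.498) = 64%.

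For assumed totals of 20 and 100 tests, Bonferroni power is Φ(2.854 − 3.023) = 43% and Φ(2.854 − 3.481) = 27%.

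**3. Unadjusted screen.** False share of significant pairs = (1−p1)·0.05 / [(1−p1)·0.05 + p1·0.814].

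| p1 (assumed) | False share |
|---|---|
| 2% | 0.0490/(0.0490 + 0.0163) = 75% |
| 5% | 0.0475/(0.0475 + 0.0407) = 54% |
| 10% | 0.0450/(0.0450 + 0.0814) = 36% |

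**4. Screen under Benjamini-Hochberg, q=0.10.** For many tests, the per-test cut-off a solves a = q·[(1−p1)·a + p1·power(a)]. With p1=5%, a = 0.00235 and average power is 43%. Simulation with independent tests gives about 54%, 46% and 43% for 20, 100 and 300 tests. With null taxa correlated at 0.3 to 0.6 the results are similar: 55–56%, 47–49% and 45%.

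**5. Detectable r at 80% average power, n=30.** a = 0.8·q·p1/(1 − q(1−p1)); r = tanh((z + 0.842)/√27), with z the two-sided critical value at a.

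| p1 (assumed) | q=0.05 | q=0.10 |
|---|---|---|
| 10% | a=0.0042, r=0.61 | a=0.0088, r=0.58 |
| 2% | a=0.0008, r=0.67 | a=0.0018, r=0.64 |

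**6. The pilot.** With n=14 and no association, r=0.5 corresponds to t = 0.5·√(12/0.75) = 2.00 on 12 df. By chance, 3.4% of taxa exceed +0.5, and 6.9% exceed 0.5 in absolute value (roughly normal data assumed). The reported figure is 5%.

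Whether 5% exceeds chance depends on how many taxa there were and how correlated they are, and the documents give neither. For independent null taxa, the binomial chance that at least 5% of them exceed +0.5 is about 25% at 50 taxa, 15% at 200, 4% at 500 and 0.6% at 1,000. With taxa correlated at 0.3 it is about 22% even at 500 and 1,000.

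**The case against.** The strongest case is that this is a proof-of-concept study whose primary aim is technical feasibility, that the association is secondary, and that the power sentence already reads as one test. All of that is true, and it limits the weight of the point. It does not close the gap: Section 1.1 attaches the proof-of-concept label to the primary objective, no section calls the microbiota associations exploratory, and Section 11.0 gives them a formal power statement that carries the whole sample size.

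It is also fair that the size of the screen is not in the documents. The results for 20 or more tests, the false shares and the detectable correlations are therefore illustrations across assumed ranges, and the detectable r depends on the q chosen. The four-day result for one pair does not rest on these assumptions.

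Four stronger readings are tempting, and the documents do not support them:

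- **The 80% is miscalculated.** It reproduces.
- **30 participants are too few.** If one pair and one day or summary are named, 81.4% stands at n=30.
- **Every pair will be declared at 5%.** That level appears only in the sample-size calculation, so false associations on this scale are possible but not planned.
- **The pilot result is noise.** With many independent taxa, 5% would be more than chance readily gives. The sponsor has the data to settle this; the documents do not.

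**Conclusion.** The concern holds and should be fixed. Section 11.0 gives a correct per-test power without identifying the test, for an open set of taxa, indices, SCFAs and days, with no multiplicity rule. The firm part is that the 81.4% applies to one unnamed test and falls to 64% once a single pair is tested on all four days with Bonferroni.

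The wider figures are conditional. The 75% to 36% false share assumes that 2% to 10% of pairs truly have r=0.5. The 43% under Benjamini-Hochberg assumes q=0.10, 5% real pairs and a large number of tests; smaller screens do somewhat better.

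On the pilot, the conclusion is limited to this: 5% of taxa above 0.5 in 14 people does not by itself show that r=0.5 is achievable. The section's other ground, the stated importance of r=0.5, is untouched, and so is the feasibility objective.

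**What to change.** In Section 11.0:

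1. State that the 80% is per-test power. Then, before sequencing data are analysed, either name the one microbiota measure, the one SCFA and the day or day-summary to which it applies, or label the whole screen exploratory and say that the 80% does not apply to it.
2. For all other microbiota correlations, with SCFAs and with fecal inulin (objective 1.2.3), control the false discovery rate at a stated q, report the number of tests, and label them exploratory.
3. State the detectable r for the chosen q with its assumptions. For 10% to 2% real pairs it is about 0.61–0.67 at q=0.05 and 0.58–0.64 at q=0.10.
4. Do not rest achievability on the pilot percentage alone. Report the pilot's number of taxa, check the observed 5% against chance allowing for correlation between taxa, and rest r=0.5 on its stated importance.

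**Cost.** A few sentences, a short adjustment step in the analysis code, and the scientific work of choosing a defensible pair and summary over days if that option is taken. No extra participants, samples or procedures. The downside is that fewer taxa will be called significant and the stated power for the screen will be less favourable.

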12.0 Statistical Data Management

All study data will be recorded onto an electronic database (REDCap) which will be accessible only by certified research personnel. Only de-identified anonymized data will be analyzed. Quality assurance steps will include: built in range checks, testing of the database prior to

moving to production mode. The following quality control methods will be used: extraction and cleaning of data every 6 months.

13.0 Privacy/Confidentiality Issues

Potential risks include breach of confidentiality or invasion of privacy. To minimize risk of loss of confidentiality, participant records will be assigned a unique identifier in a coded manner accessible only by study personnel. All data collected on paper will be kept in a locked drawer within the GI Research Office until data collection is complete and transferred to an electronic storage system, after which papers will be discarded and destroyed. Data will also be captured and stored electronically in REDCap and in a protected Microsoft Excel spreadsheet on a Department Server. The storage location will be backed up manually every month. Electronic data will be automatically exported to common statistical packages such as SPSS, SAS, Stata, R/S-Plus at the time of conducting analyses. Only de-identified or anonymized clinical data will be transferred processing laboratories.

14.0 Follow-up and Record Retention

The study is expected to last 24 months in duration. All electronic records will be retained indefinitely. All data collected on paper will be kept in a locked drawer within the GI Research Office until data collection is complete and transferred to an electronic storage system, after which papers will be discarded and destroyed.

